8.4 Pharmacokinetics

Venous blood samples will be collected in appropriately labeled tubes, at the times specified in the Schedule of Assessments ([Section 1.3](#)), to evaluate the PK of emraclidine and its metabolite CV-0000354. Additional details about sample collection, processing, and shipment will be provided in the Lab Manual.

All PK samples should be obtained at the exact nominal time relative to dosing. Samples obtained within 20% of the nominal time point (eg, within 12 minutes of a 60-minute sample) will not be considered a protocol deviation, as long as the exact time of sampling is captured in the source documents.

A fully validated bioanalytical method will be used to quantitate the concentrations of emraclidine and CV-0000364 (metabolite) in plasma. Plasma samples collected in this trial may be used to further development of the bioanalytical method or identification of metabolites. The backup plasma samples may be stored for a duration of approximately up to 1 year after the date of the final clinical study report.

Plasma concentration data from this trial combined with other data may also be used to build and/or update a population PK model for emraclidine for the purpose of further characterizing the PK or PK/pharmacodynamic behavior of the compound. Any population PK assessment will be described in a separate report.

Statistical analyses for PK parameters are summarized in [Section 9.3.6](#).

8.5 Biomarkers

Biomarkers are not evaluated in this trial.

8.6 Future Biospecimen Research

Studying the variation in genetic markers and other biomarkers may help to explain some of the variability in response seen with some drugs among different individuals. This is referred to as pharmacogenomic/biomarker research. Comparing the DNA, RNA, protein, and metabolite variation patterns of participants who respond well and those who respond poorly to treatment may help to better define the most appropriate group of participants in which to target a given treatment. Collecting biospecimens for exploratory pharmacogenomic/biomarker analyses and retaining them at Cerevel makes it possible to better understand the drug's mechanism of action and to seek explanations for differences in, for example, exposure, pharmacodynamics, tolerability, or safety not anticipated prior to the beginning of this trial.

Future biospecimen research samples will be collected from participants who provide additional consent specifically for this sample collection. Research performed on these samples may include genetic analyses, gene expression profiling, proteomics, metabolomics and/or the measurement of other analytes. Such research is for biomarker testing to address emergent questions not described elsewhere in the protocol (as part of the main trial). The objective of collecting these specimens is to explore and identify biomarkers that inform the scientific understanding of diseases or their therapeutic treatments.

Additional details about future biospecimen research samples are provided in [Section 10.5](#).

8.7 Health Economics and Resource Utilization

8.7.1 Short Form – 6 Dimensions Version 2.0

The SF-6D is a new, internationally adopted measure for assessing the cost-effectiveness of health care interventions. The SF-6D was developed by reducing the SF-36 to a 6-dimension classification (physical functioning, role participation, social functioning, bodily pain, mental health, and vitality) and developing an algorithm to generate a continuous index for health ([Brazier et al, 2002](#)). The algorithm shows how much value people place on different health limitations, and how they will trade-off between them; for example, how much vitality a patient will sacrifice for a reduction in pain. Version 2.0

of the SF-6D (SF-6Dv2) is an improved version of the SF-6D, the SF-6Dv2 classification system describes more distinct levels of health than SF-6D, changes the descriptions used for a number of dimensions, and provides clearer wording for health state valuation (Brazier et al, 2020).

9 STATISTICAL CONSIDERATIONS

9.1 Statistical Hypotheses

The primary hypotheses are summarized below. The tests will be conducted in hierarchical order from H_1 to H_2 at a 2-sided α level of 0.05. If both primary hypotheses H_1 and H_2 are successful, the key secondary endpoint of change from baseline CGI-S at Week 6 will be similarly tested in hierarchical order with respect to the 2 doses. The overall type I error rate thus is maintained at the 0.05 level.

Primary Endpoint	Emraclidine 30 mg QD vs Placebo	Emraclidine 15 mg QD vs Placebo
Change from Baseline to Week 6 in PANSS total score	$H_1 : \mu_{\text{active}} = \mu_{\text{placebo}}$ vs $\mu_{\text{active}} \neq \mu_{\text{placebo}}$	$H_2 : \mu_{\text{active}} = \mu_{\text{placebo}}$ vs $\mu_{\text{active}} \neq \mu_{\text{placebo}}$

Abbreviations: PANSS=Positive and Negative Syndrome Scale; QD=once daily.

9.2 Analysis Sets

The analysis sets that are defined for this trial are described in [Table 6](#).

Table 6 Analysis Set Descriptions

Population	Description	Analysis
ITT	All randomized participants	Demographic and Baseline Characteristics
FAS	All randomized participants who receive at least 1 dose of IMP. This will be the safety analysis set.	Safety analysis
mITT	All randomized participants who receive at least 1 dose of IMP and have both a baseline and at least 1 postbaseline PANSS assessment	Primary analysis set for efficacy
Endpoint completers	All participants in the mITT population who complete the PANSS assessment at Week 6	Sensitivity analysis for efficacy
PK Analysis Set	All randomized participants who receive at least 1 dose of IMP and have at least 1 measurable emraclidine concentration	PK analysis

Abbreviations: FAS=full analysis set; IMP=investigational medicinal product; ITT=intent-to-treat; mITT=modified intent-to-treat; PANSS=Positive and Negative Syndrome Scale; PK=pharmacokinetic.

9.3 Statistical Analyses

9.3.1 General Considerations

Descriptive statistical methods will be used to summarize the data from this trial, with statistical testing performed for the efficacy endpoints. All statistical analyses will be conducted with the SAS® System, version 9.4 or higher. The remainder of this section is a summary of the planned statistical analyses of the primary and secondary endpoints as well as a description of planned safety analyses. Full details of these analyses will be included in the statistical analysis plan.

9.3.2 Primary Endpoint/Estimand Analyses

The primary estimand has the following attributes:

1. Treatments as randomized
2. mITT population as the primary population of interest
3. Change from Baseline to Week 6 in total PANSS score as the primary endpoint of interest
4. The population level summary of interest is the treatment differences estimated based on the least square mean and the corresponding 95% confidence interval from the MMRM model with treatment, visit, and treatment by visit interaction as fixed effect, participant as a random effect, and baseline PANSS score as a covariate. An unstructured covariance structure will be used for the repeated measures. The Kenward-Roger approximation will be used to estimate the denominator degrees of freedom. If the unstructured covariance matrix results in convergence issue, the heterogeneous Toeplitz covariance structure followed by the heterogeneous first-order autoregressive (AR(1)) structure will be used. If a reduced covariance matrix becomes necessary, the sandwich variance estimator will be used.
5. To address ICEs with the primary outcome data available, a treatment policy strategy will be used to include all collected outcomes in the primary statistical analysis, consistent with the intent-to-treat principle. The only exception will be the cases of concomitant use of protocol prohibited other antipsychotic and, in such cases, the data collected under the influence of confounding ICEs will be treated as missing.
6. To address ICE of trial or treatment discontinuation with no outcome data collected post discontinuation, the primary analysis of MMRM described above will be followed by PMM approach with varying level of shift parameters for missing values due to discontinuations that are potentially missing not at random (MNAR), including discontinuation due to lack of efficacy or due to adverse events. This will be implemented using delta adjustment imputation method. Further details will be described in the SAP.

The statistical hypothesis testing on the primary endpoint (H_1 and H_2 above) will be based on the estimated treatment difference from the model at Week 6. The evaluation of other time points will also be derived from the same model.

The number and proportion of responders (ie, participants with 30% reduction from Baseline in the PANSS total score at Week 6 or the last assessment before discontinuation) will be summarized. A logistic regression model, with baseline PANSS as a covariate, will be used to compare the proportion of responders in each active arm with placebo. If expected counts are < 5 , then a Fisher's Exact test will be used.

9.3.3 Secondary Endpoint/Estimand Analyses

The secondary estimand has the following attributes:

1. Treatments as randomized
2. mITT population as the population of interest
3. Change from Baseline to Week 6 in CGI-S score as the endpoint of interest
4. The population level summary of interest is the treatment differences estimated based on the least square mean and the corresponding 95% confidence interval from the MMRM model with treatment, visit, and treatment by visit interaction as fixed effect, participant as a random effect, and baseline CGI-S score as a covariate. An unstructured covariance structure will be used for the repeated measures. If the unstructured covariance matrix results in convergence issue, the heterogeneous Toeplitz covariance structure followed by the heterogeneous first-order autoregressive (AR(1)) structure will be used. When a reduced covariance matrix is used, the sandwich variance estimator will be used. The Kenward-Roger approximation will be used to estimate the denominator degrees of freedom.
5. ICEs will be addressed using the same strategies as described above for the primary endpoint

The number and proportion of participants with ≥ 1 and ≥ 2 point improvements from Baseline at the last CGI-S assessment (at Week 6 or the last assessment before discontinuation) will be summarized. A logistic regression model, with baseline CGI-S as a covariate, will be used to compare the proportion of responders in each active arm with placebo. If expected counts are < 5 , then a Fisher's Exact test will be used.

9.3.4 Other Endpoints

Other endpoints, including change from Baseline in BACS and SF-6D measurements, will be analyzed similarly using MMRM models.

9.3.5 Safety Analyses

Treatment-emergent adverse events will be coded according to MedDRA and summarized by treatment group, system organ class, and preferred term. Further summaries will be done by seriousness, severity, and relationship to IMP.

Heart rate and blood pressure measurements will be taken weekly at approximately 2 hours after IMP administration. The weekly measurements and corresponding changes from Baseline will be summarized by descriptive statistics. The change from Baseline will be analyzed using MMRM with treatment group, visit, and treatment by visit interaction as fixed effects and participant as a random effect, with the baseline value as a covariate. The difference between each emraclidine group versus placebo at each week will be estimated based on the least squares mean from the MMRM with the 95% CIs.

Other safety endpoints will be summarized with descriptive statistics by treatment group, including clinical laboratory assessments and metabolic parameters, and physical and neurological examination results (including body weight), suicidality assessments using C-SSRS, and EPS assessed by AIMS, SAS, and BARS.

9.3.6 Other Analyses

Plasma concentrations of emraclidine and its major metabolite (if required) will be summarized by dose, visit, and nominal time (if applicable). All PK exposure-response analyses will be described in a separate PK analysis plan that will be finalized before database lock.

Plasma concentrations will also be pooled with data from other trials in a population PK analysis to describe the time course of plasma concentrations of emraclidine and the influence of covariates (eg, body weight, age, sex, race, concomitant medications). The results of population PK analysis and response-exposure analyses will be presented separately from the main clinical study report.

9.4 Interim Analyses

No interim analysis is planned.

9.5 Sample Size Determination

A sample size of approximately 93 participants in each treatment group completing the Week 6 assessments (approximately 279 in total) should provide at least 90% power to detect an effect size of 0.48 in change from Baseline in PANSS total score at Week 6 between either active treatment group versus placebo at the $\alpha=0.05$ level. The effect size of 0.48 represents a clinically meaningful effect on symptom reduction based on large scale meta-analysis of historical data from several currently approved antipsychotic medications in common usage ([Leucht et al, 2013](#)). It could be translated into a difference of 7 points versus placebo if the standard deviation of change from baseline is 14.6 points or a difference of 8 points versus placebo if the standard deviation of change from

baseline is 16.7 points. Both scenarios of the standard deviation are consistent with historical observations. To account for a discontinuation rate of approximately 25% for a 6-week treatment period (as observed in Trial CVL-231-SCH-001), it is planned to randomize approximately 372 participants.

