Participants may be allowed to stay in the inpatient facility up to 1 week after their last dose of IMP if necessary to achieve stabilization on alternate therapy with review and approval by the medical monitor.

All participants (completers and early withdrawals), with the exception of those entering the optional open-label rollover trial, will have a follow-up safety contact at approximately 28 days after the last dose of IMP.

Number of Participants:

Approximately 600 participants will be screened to achieve approximately 372 participants qualified to be randomized to treatment in the trial (124 per treatment group).

In the event of higher than anticipated early terminations, Cerevel may extend enrollment in order to achieve trial objectives.

Key Entry Criteria:

- Men and women 18 to 65 years of age, inclusive, with a primary diagnosis of schizophrenia per the Diagnostic and Statistical Manual of Mental Disorders, Fifth Edition, as confirmed by the Mini International Neuropsychiatric Interview for Psychotic Disorders, and experiencing an acute exacerbation or relapse of psychotic symptoms, with onset less than 60 days prior to signing the informed consent form
- PANSS total score between 85 and 120, inclusive, and CGI-S ≥ 4 (moderately to severely ill) at the time of signing the informed consent form and at Baseline

Intervention Groups and Duration:

Participants will receive treatment with 1) emraclidine 15 mg QD, 2) emraclidine 30 mg QD, or 3) placebo during the Treatment Period of the trial.

The trial will include up to a 15-day Screening Period, a 45-day Inpatient Treatment Period, and a 28-day Follow-up Period. Each participant will participate in the trial for up to approximately 13 weeks.

Statistical Considerations:

Sample Size Estimation:

A sample size of approximately 93 participants in each treatment group completing the Week 6 assessments (approximately 279 in total) should provide at least 90% power to detect an effect size of 0.48 in change from Baseline in PANSS total score at Week 6 between either active treatment group versus placebo at the $\alpha=0.05$ level. The effect size of 0.48 represents a clinically meaningful effect on symptom reduction based on large scale meta-analysis of historical data from several currently approved antipsychotic

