6. To address ICE of trial or treatment discontinuation with no outcome data collected post discontinuation, the primary analysis of MMRM described above will be followed by pattern mixture model (PMM) approach with varying level of shift parameters for missing values due to discontinuations that are potentially missing not at random (MNAR), including discontinuation due to lack of efficacy or due to adverse events. This will be implemented using delta adjustment imputation method. Further details will be described in the statistical analysis plan (SAP).

The statistical hypothesis testing on the primary endpoint (emraclidine 30 mg QD vs placebo and emraclidine 15 mg QD vs placebo) will be based on the estimated treatment difference from the model at Week 6 and will be tested in a hierarchical order with each at 2-sided alpha level 0.05. The evaluation of other time points will also be derived from the same model.

The number and proportion of responders (ie, participants with 30% reduction from Baseline in the PANSS total score at Week 6 or the last assessment before discontinuation) will be summarized. A logistic regression model, with baseline PANSS as a covariate, will be used to compare the proportion of responders in each active arm with placebo. If expected counts are <5, then a Fisher's Exact test will be used.

The secondary estimand has the following attributes:

1. Treatments as randomized
2. mITT population as the primary population of interest
3. Change from Baseline to Week 6 in CGI-S score as the endpoint of interest
4. The population level summary of interest is the treatment differences estimated based on the least square mean and the corresponding 95% confidence interval from the MMRM model with treatment, visit, and treatment by visit interaction as fixed effect, participant as a random effect, and baseline CGI-S score as a covariate. An unstructured covariance structure will be used for the repeated measures. If the unstructured covariance matrix results in convergence issue, the heterogeneous Toeplitz covariance structure followed by the heterogeneous first-order autoregressive (AR(1)) structure will be used. When a reduced covariance matrix is used, the sandwich variance estimator will be used. The Kenward-Roger approximation will be used to estimate the denominator degrees of freedom.
5. ICEs will be addressed using the same strategies as described above for the primary endpoint.

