## 1.2. Sample Size Considerations

A sample size of approximately 93 subjects in each treatment group completing the Week 6 assessments (approximately 279 in total) should provide at least 90% power to detect an effect size of 0.48 in change from Baseline in the Positive and Negative Symptom Score (PANSS) total score at Week 6 between either active treatment group versus placebo at the  $\alpha=0.05$  level. The effect size of 0.48 represents a clinically meaningful effect on symptom reduction based on large scale meta-analysis of historical data from several currently approved antipsychotic medications in common usage ([Leucht et al, 2013](#)). It could be translated into a difference of 7 points versus placebo if the standard deviation of change from baseline is 14.6 points or a difference of 8 points versus placebo if the standard deviation of change from baseline is 16.7 points. Both scenarios of the standard deviation are consistent with historical observations. To account for a discontinuation rate of approximately 25% for a 6-week treatment period (as observed in Trial CVL-231-SCH-001), it is planned to randomize approximately 372 subjects.

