## 5.4. Multiplicity Adjustment

A graphical approach depicted below illustrates the hierachal multiple testing strategy planned for the hypotheses described above to control the overall Type I error rate. The primary endpoint of the emraclidine 30 mg QD will be compared with that of placebo ( $H_1$ ) with full  $\alpha$  of 0.05 and, if successful, the available  $\alpha$  will be passed along fully ( $r=1$ ) to the comparison of the primary endpoint of emraclidine 15 mg QD with placebo ( $H_2$ ). If  $H_2$  is successful, the full  $\alpha$  will be available to the secondary hypothesis  $H_3$ . The sequence will continue until  $H_4$  or until the sequence breaks with no  $\alpha$  remaining available.

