### **5.9.2. Main Analytical Approach**

The change from baseline to each study visit in total PANSS score will be summarized by visit and treatment group. A MMRM analysis will be used to analyze the data from all post-randomization timepoints up to Week 6 with treatment, geographic region, visit, and treatment by visit interaction as fixed effect, subject as a random effect, and baseline PANSS score as a covariate. An unstructured covariance structure will be used for the repeated measures. If the unstructured covariance matrix results in convergence issue, the heterogeneous Toeplitz covariance structure followed by the heterogeneous first-order autoregressive (AR(1)) structure will be used. The Kenward-Roger approximation will be used to estimate the denominator degrees of freedom. The difference between each emraclidine dose group and placebo at Week 6 will be estimated based on the Least Squares Mean (LSMean) difference between the treatment groups at Week 6 from the MMRM with the associated 95% confidence interval (CI) and P-value. A Cohen's D value will be derived as the ratio of the estimated difference to the population standard deviation at each visit estimated from the model (the square root of the diagonal elements of the estimated covariance matrix). The missing values are assumed to be missing at random for the main analysis, including missing due to missed visits or early termination due to COVID-19 control measures. The LSM ( $\pm$ SE) from the model will be plotted for change in PANSS total score by visit and treatment group. Similarly, the mean ( $\pm$ SD) of absolute values and change from Baseline PANSS total score will be presented by visit and treatment group.

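### The 90% power stated for either dose is a single-comparison figure; under the planned test order 15 mg has about 84% on the same basis if both effects are 0.48

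*Protocol*

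**What the plan says.** The power statement appears three times with the same figures: Protocol 9.5, the Protocol synopsis ("should provide at least 90% power to detect an effect size of 0.48 in change from Baseline in PANSS total score at Week 6") and SAP 1.2 ("should provide at least 90% power to detect an effect size of 0.48"). About 93 completers per group are planned. The comparison is described as one "in change from Baseline in PANSS total score at Week 6 between either active treatment group versus placebo", at alpha 0.05. With 25% discontinuation this leads to 124 randomized per group and 372 in total.

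The test procedure is set out elsewhere. The synopsis says that the two dose comparisons "will be tested in a hierarchical order with each at 2-sided alpha level 0.05". Protocol 9.1 fixes the order: "The tests will be conducted in hierarchical order from" H1 (30 mg versus placebo) to H2 (15 mg versus placebo). SAP 5.4 gives H1 the full 0.05 and passes it "to the comparison of the primary endpoint of emraclidine 15 mg QD with placebo" only if H1 succeeds. The key secondary CGI-S hypotheses open only after both H1 and H2 have succeeded.

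None of the three sample size paragraphs says that its figure is per comparison or that it leaves the test order out of account. No power is given for 15 mg within the sequence, or for both doses together.

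**The concern.** Under a fixed sequence, the power of the second hypothesis is the probability that the first and second tests both succeed. That cannot exceed the second test's stand-alone power, and it falls clearly below it unless the first test is almost certain to succeed. The plan gives one figure for both doses, so 15 mg is credited with a chance of confirmatory success that the procedure does not deliver on the basis used to compute the figure.

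H2 is one of the two primary hypotheses, and a reader of the sample size section would take at least 90% as its chance of success. The same joint probability is also the chance that CGI-S can be formally tested at all, and the plan does not state it.

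What is at stake is an accurate statement of the trial's operating characteristics. Type I error control is not in question, and the 15 mg estimate, confidence interval and p-value will be reported whatever happens to H1 (SAP 5.9.2: "The difference between each emraclidine dose group and placebo at Week 6 will be estimated").

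**Working it through.** **Inputs from the documents**

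- Effect size d = 0.48; the two scenarios are 7/14.6 = 0.479 and 8/16.7 = 0.479 (Protocol 9.5, SAP 1.2)
- Completers per arm n = 93; randomized per arm 124, so 31 expected dropouts per arm (Protocol 9.5, 4.1.2)
- Two-sided alpha 0.05, 30 mg first, then 15 mg (Protocol 9.1, SAP 5.3 and 5.4)
- Allocation 1:1:1 with one placebo arm (Protocol 4.1.2). With equal arms, the shared placebo mean gives the two test statistics a correlation of 0.5.

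**Step 1: reproduce the stated figure**

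The mean of the test statistic is d × √(n/2) = 0.48 × √(93/2) = 3.273. Power is Φ(3.273 − 1.960) = Φ(1.313) = 90.5%; the noncentral t gives 90.3%. With 92 per arm the t-based power is 89.9%, so 93 is the right number. Dropout: 93/(1 − 0.25) = 124 per arm, 372 in total. The stated figures are correct for one comparison, and therefore for 30 mg.

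The wording cannot mean at least one dose: the chance that at least one of the two pairwise tests is nominally significant is 2 × 0.9054 − 0.8408 = 97.0%.

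**Step 2: 15 mg under the sequence**

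Power for H2 = P(Z₁ > 1.96 and Z₂ > 1.96), where (Z₁, Z₂) is bivariate normal with both means 3.273, unit variances and correlation 0.5. The result is **84.1%**. A 400,000-run simulation with t tests gives 83.7% (pairwise variances) and 83.9% (pooled variance). The gap to the single comparison is 0.9054 − 0.8408 = 0.0646, or 6.5 points.

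**Step 3: dependence on the 30 mg effect** (15 mg at 0.48, 93 per arm; the 30 mg values other than 0.48 are assumptions)

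| 30 mg effect | 15 mg power in sequence |
|---|---|
| 0.40 | 73.6% |
| 0.48 | 84.1% |
| 0.55 | 88.3% |
| 0.60 | 89.7% |
| about 0.62 | 90% |

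**Step 4: dependence on information recovered from dropouts**

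The primary analysis uses partial data (SAP 5.9.2: "A MMRM analysis will be used to analyze the data from all post-randomization timepoints up to Week 6"), and the documents do not say how much Week 6 information this recovers. The range, with both effects at 0.48 and before any gain from baseline adjustment, is:

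| Effective n per arm | Single comparison | 15 mg in sequence | Gap (points) |
|---|---|---|---|
| 93 (nothing recovered) | 90.5% | 84.1% | 6.5 |
| 109 (about half of the 31 dropouts) | 94.3% | 90.1% | 4.2 |
| 124 (everything recovered) | 96.6% | 93.8% | 2.7 |

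Sequence power reaches 90% at an effective n of 108.6, which means recovering 108.6 − 93 = 15.6 of the 31 dropouts per arm. With no recovery, a correlation of √(1 − 93/108.6) = 0.38 between baseline and change would have the same effect. The documents give neither quantity.

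**The case against.** The strongest reply is that the sentence is a conventional per-comparison statement and is true as such. The hierarchy is disclosed in the same synopsis, in Protocol 9.1 and in SAP 5.3 and 5.4, so an informed reader can combine the two. The sample size contains no arithmetic error. This is fair as far as it goes, but nothing in the three paragraphs labels the figure as per comparison, and the words at least present it as a floor. On the plan's own completers-only basis, 15 mg is below that floor.

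A second reply is that 84% is the bottom of the information range. The planned MMRM uses partial data and adjusts for baseline. Recovering a quarter of the dropout information (93 + 31/4 = 100.75 per arm) together with a baseline-change correlation of about 0.27 would already bring 15 mg to 90%. This stands: it cannot be shown that 15 mg has less than 90% under the analysis actually planned. But the stated 90% is itself a completers-only figure, so the like-for-like comparison is 84.1% with 90.5%, and a gap remains at every effective n.

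Third, the 30 mg effect may well exceed 0.48. The Phase 1b difference of 12.7 points (Protocol 2.2.3), divided by the planning SDs of 16.7 and 14.6, is 0.76 to 0.87. At those values the sequence costs almost nothing, and 15 mg has 90.5% at its own effect of 0.48. This also stands as a conditional statement. However, that estimate comes from 27 participants on 30 mg, and the sample size section assumes 0.48, with no larger value for 30 mg.

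**Conclusion.** The concern holds. At least 90% is right for 30 mg. For 15 mg it is the stand-alone figure; under the plan's own procedure and on the plan's own basis the figure is about 84%. This rests on both effects being 0.48, 93 completers per arm, a correlation of 0.5 from the shared placebo arm, and no credit for partial data or baseline adjustment. The actual MMRM power of either dose cannot be computed from the documents and may be higher.

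This is a misstated operating characteristic for a primary hypothesis, repeated in three places. It should be corrected, but it is not a design flaw: the sample size, alpha allocation and analysis can all stand.

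**What to change.** In the synopsis, Protocol 9.5 and SAP 1.2, replace the wording that gives one figure for either dose with text along these lines:

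> At least 90% power for 30 mg versus placebo (H1); about 84% for 15 mg versus placebo (H2) under the hierarchical procedure if both effects are 0.48. Both figures are completers-only and unadjusted. The 15 mg figure rises towards 90% if the 30 mg effect is larger and falls if it is smaller.

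The cost is one sentence in three places and a less favourable stated figure for 15 mg. Two of the places are in the Protocol, where amendments need IRB/IEC approval (Protocol 10.1.1), so the Protocol wording could be changed at the next amendment. A label saying only that the 90% applies to each pairwise comparison before the hierarchy would remove the ambiguity, but would still leave 15 mg without a power figure under the planned procedure.
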